
	
LM on MRI), or non-PR, non-PD (continued presence of evidence of LM on MRI). PD for LM will not be defined by MRI.
 
The response efficacy endpoints will be evaluated separately for peripheral disease, for BM, and for LM, and a summary response will also be derived (See Table 14-1). For LM, if positive CSF cytology and MRI diagnostic findings were both present at screening, CR requires the absence of LM by both modalities. Best overall response, duration of response, and duration of stable disease will be reported, based on the examples in Table 14-1. PFS, rate of CNS non-progression at 3 and 6 months, non-CNS TTP, and CNS TTP, and OS also will be assessed.
 
Subjects with limited CNS or extra-CNS disease progression (oligoprogressive disease) may receive local ablative therapy (radiation therapy or surgery) and then be continued on tesevatinib. This practice is consistent with data indicating that some patients with NSCLC on TKI therapy who have oligoprogressive disease appear to have significant periods of additional disease control with this approach.¹⁶ Any such patients will be considered to have disease progression for analyses of PFS and for analyses of progression in the relevant (CNS or extra-CNS) compartment at the time of detection of oligoprogressive disease.
 
Subjects with scans that are on the “borderline” of disease progression (e.g. 21% increase in sum of target lesion diameters or equivocal findings on CSF cytology or MRI) but for whom the investigator determines a clinical benefit may occur in the study. These subjects will be allowed to continue in the study after discussion with the medical monitor. If improvement is documented at the next subsequent staging time point (e.g. 17% increase in sum of target lesion diameters or stable CNS symptoms), the subject will continue on study. If worsening is documented (e.g. 30% increase in sum of target lesion diameters or worsening of CNS symptoms), the subject should be discontinued from the study, and the progression date should be the original date on which “borderline” disease progression was first documented. If stable, then they will be followed until improvement or worsening occurs.

Quality of Life	
QOL will be evaluated via the EORTC QLQ-C30 and EORTC QLQ-BN20 questionnaires administered at Screening, on Day 1 of Cycle 3, and on Day 1 of odd-numbered cycles thereafter.

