- c: Safety labs = hematology and clinical chemistry and urinalysis. Note that Cycle 1 Day 1 labs need not be repeated if screening visit occurred within 4 days prior to Day 1 visit. Safety labs will also be done at C2D15, C3D15, C4D15, C5D15, and C6D15; they are to be done locally and will include serum chemistry only. There will be a 3 day window for the D15 chemistry labs. Cystatin C does not need to be included in the chemistry labs done on C2D15, C3D15, C4D15, C5D15, and C6D15.
 - d: Pregnancy tests will be done using urine samples in women of childbearing potential. Subject must have a negative urine pregnancy test documented within the 24-hour period prior to the first dose of study drug. Confirm with serum testing if urine sample is positive..
 - e: Supine 12-Lead ECGs will be performed at screening; Days 1, 7 and 14 of Cycle 1; on Day 1 of Cycles 2 and Day 1 of each Cycle including at End of Study Drug Treatment visit Assessment to be performed at predose, and once within 4 – 8 hours postdose for Days 1, 7 and 14 of Cycle 1. At each timepoint, repeat ECG three times consecutively within 30 minutes (must have an interval of at least 1–2 minutes between ECGs).
 - f: Tumor assessment is to be performed at screening, at C2D1, on C3D1, and after every 2 cycles (beginning on Day 1 of Cycle 3 [\pm 7 days]). Tumor assessment should include brain MRI. Peripheral (non-CNS) tumor may be assessed with either CT or MRI, but method of assessment should be the same throughout the study. Tumor assessment on C2D1 will be limited to brain MRI.
 - g: Bone scans are to be performed at screening and then as clinically indicated.
 - h: Tesevatinib will be administered at the dose of 300 mg once daily.
 - i: EORTC QLQ-C30 and EORTC QLQ-BN20 questionnaires administered at screening, on Day 1 of Cycle 3, and on Day 1 of odd-numbered cycles thereafter and EOS
 - j: AEs are to be collected from the time of informed consent through 30 days after last dose of study drug.
 - k: The End-of-Study Drug Treatment visit is to occur within 3 days after the subject's last dose of study drug. This may occur at the visit at which disease progression is diagnosed. Tumor assessment does not need to be performed if it was performed in the previous 8 weeks.

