9.1.14 Quality of Life Questionnaires

QOL will be evaluated using the European Organization for Research and Treatment of Cancer (EORTC) EORTC QLQ-C30 and EORTC QLQ-BN20 questionnaires administered at screening, on Day 1 of Cycle 3, on Day 1 of odd-numbered cycles thereafter, and at the EOS visit. Samples of the questionnaires are located in Appendix G and Appendix H.

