9.2.10 End-of-Study Drug Treatment Visit

Subjects are to return to the study site within 3 days after the subject's last dose of study drug to complete all end-of-study drug treatment assessments as described below. This may occur at the visit at which disease progression is diagnosed.

- Complete physical examination, including weight
- Vital sign measurements (sitting blood pressure, pulse, respiratory rate, temperature)
- ECOG Performance status

-
- Leptomeningeal metastasis symptom assessment – Cohort B only.
 - Hematology, serum chemistry, and urinalysis
 - Urine pregnancy test, if applicable (positive results to be confirmed by serum pregnancy testing)
 - Supine 12-Lead ECG (repeat three times consecutively within 30 minutes [must have an interval of at least 1-2 minutes between ECGs])
 - Tumor assessment (brain MRI, thoracic and abdominal CT/MRI) (only required if one hasn't been performed in the previous 8 weeks)
 - Quality of Life Questionnaire
 - Concomitant medications
 - AE assessment
 - Final return and accounting of study drug

9.2.11 30-Day Follow-Up

The 30-Day Follow-Up should occur 30 days (\pm 5 days) after the subjects' last dose of tesevatinib, but prior to starting new therapy. This may occur prior to 30 days if new therapy is started within 30 days of last dose of study drug.

- Complete physical examination, including weight
- Vital sign measurements (sitting blood pressure, pulse, respiratory rate, temperature)
- ECOG Performance status
- Hematology, serum chemistry, and urinalysis
- Urine pregnancy test, if applicable (positive results to be confirmed by serum pregnancy testing)
- Concomitant medications
- AE assessment

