### Secondary objectives:

- To evaluate changes in Quality of Life (QOL) in subjects receiving tesevatinib for BM.
- To determine the median progression-free survival (PFS), rate of central nervous system (CNS) non-progression at 3 and 6 months, non-CNS time to progression (TTP), and CNS TTP.
- To determine the median overall survival (OS).

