## Secondary objectives:

- To evaluate the activity of tesevatinib in subjects with NSCLC, EGFR activating mutations and LM as measured by decreases in NSCLC cells in the cerebrospinal fluid (CSF) using standard cytology.
- To evaluate the activity of tesevatinib in subjects with NSCLC, EGFR activating mutations and LM as measured by improvement in CNS magnetic resonance imaging (MRI) findings.
- To evaluate the pharmacokinetics (PK) of tesevatinib in CSF versus plasma.
- To evaluate changes in QOL in subjects receiving tesevatinib for LM.

- To determine the median PFS, rate of CNS non-progression at 3 and 6 months, non-CNS TTP, and CNS TTP.
- To determine the median OS.

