## 1.3.1.2 Secondary endpoints

- The PFS, the OS, rate of CNS non-progression at 3 and 6 months, non-CNS TTP, and CNS TTP
- QOL will be evaluated via the European Organisation for Research and Treatment
  of Cancer Quality of Life Questionnaire (EORTC QLQ-C30) and EORTC
  QLQ-BN20 questionnaires administered at Screening, on Day 1 of Cycle 3, and on
  Day 1 of odd-numbered cycles thereafter.
- For Cohort B, decreases in NSCLC cells in the CSF using standard cytology
- For Cohort B, improvement in CNS MRI findings

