| Т     | 1.2.1  | Progression-free survival (PFS) by cohort                           | Secondary efficacy           | All treated subjects          | descriptive statistics        |
| Т     | 1.2.2  | Overall survival (OS) by cohort                                     | Secondary efficacy           | All treated subjects          | descriptive statistics        |
| Т     | 1.2.3  | non-CNS time to progression by cohort                               | Secondary efficacy           | All treated subjects          | descriptive statistics        |
| Т     | 1.2.4  | CNS time to progression by cohort                                   | Secondary efficacy           | All treated subjects          | descriptive statistics        |
| F     | 1.2.1  | Progression-free survival (PFS) by cohort                           | Secondary efficacy           | All treated subjects          | KM curve                      |
| F     | 1.2.2  | Overall survival (OS) by cohort                                     | Secondary efficacy           | All treated subjects          | KM curve                      |
| F     | 1.2.3  | non-CNS time to progression by cohort                               | Secondary efficacy           | All treated subjects          | KM curve                      |
| F     | 1.2.4  | CNS time to progression by cohort                                   | Secondary efficacy           | All treated subjects          | KM curve                      |
| Т     | 1.3.1  | QOL by visit and cohort   | Secondary efficacy           | All treated subjects          | Descriptive Statistics |
| L     | 1.4.1  | NSCLC cells in the CSF using standard cytology by visits            | Secondary efficacy           | All treated cohort B subjects | Descriptive Statistics |
| Т     | 1.4.2  | CNS MRI findings by visits and change from baseline                 | Secondary efficacy           | All treated cohort B subjects | Descriptive Statistics |
| L     | 1.4.2  | CNS MRI findings by visits  | Secondary efficacy           | All treated cohort B subjects | source date                   |
| L     | 1.5.1  | NSCLC cells in the CSF using rare cell capture techniques by visits | Exploratory Endpoints | All treated cohort B subjects | source date                   |
| L     | 1.5.2  | CSF cell-free DNA by visits   | Exploratory Endpoints | All treated cohort B subjects | source date                   |

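### The quality-of-life objective is change, but the SAP plans only by-visit summaries and its endpoint text omits the end-of-treatment questionnaire, so selective dropout could mimic improvement or hide decline

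*SAP*

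**What the plan says.** **Objective.** SAP 1.1.1 (Cohort A) states "To evaluate changes in Quality of Life (QOL) in subjects receiving tesevatinib for BM", and SAP 1.1.3 sets the same aim for Cohort C. SAP 1.1.2 (Cohort B) states "To evaluate changes in QOL in subjects receiving tesevatinib for LM". Protocol Section 6 agrees.

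**Schedule.** SAP 1.3.1.2 gives Screening, Cycle 3 Day 1 and "Day 1 of odd-numbered cycles thereafter". The Quality of Life row of the protocol synopsis (Section 4) also stops at "on Day 1 of odd-numbered cycles thereafter". Elsewhere the protocol goes further:

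- Section 9.1.14 has "on Day 1 of odd-numbered cycles thereafter, and at the EOS visit".
- The footnotes to Tables 4-1 and 4-2 have "on Day 1 of odd-numbered cycles thereafter and EOS".
- The procedure list in Section 9.2.10, for the visit within 3 days of the last dose, includes "Quality of Life Questionnaire".

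**Output.** SAP Table 1 has one QOL entry, T 1.3.1, "QOL by visit and cohort", with descriptive statistics in all treated subjects. The titles of the CNS MRI, laboratory, vital-sign and ECG tables all name change from baseline; the QOL title does not. SAP Section 2 promises descriptive statistics with 95% confidence intervals for continuous measurements in general and plans no hypothesis tests. Protocol 16.3.6 specifies change only for tumor measurements.

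**Missing data.** Protocol Section 16 rules out imputation by default. The one rule in the SAP (1.2.5) counts non-evaluable response as non-response and does not reach QOL.

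**The concern.** The planned table does not clearly answer the stated objective. A column of by-visit means describes whoever is still completing forms at each visit, so the difference between a later mean and the Screening mean mixes change within subjects with change in who is left.

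The group will shrink. Treatment normally ends at progression or unacceptable toxicity, on-cycle visits end with it, the 30-day visit has no questionnaire, and later contact is by telephone about survival and further therapy. The first on-treatment form is due only at Cycle 3 Day 1, after two 28-day cycles, while a brain MRI is already done at Cycle 2 Day 1. A subject who stops before Cycle 3 has no post-screening QOL on the schedule that SAP 1.3.1.2 lists; the EOS form is the only one.

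At stake is the reading of a secondary endpoint in uncontrolled cohorts of up to 20, where a rising mean could be reported as benefit or a real decline could be understated.

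**Working it through.** **The plan's own figures.** The documents give no QOL effect size, SD or dropout rate. Their only design figures concern response: with N = 20 and a true rate of 20%, the binomial gives P(at least 3) = 0.794 and P(at least 2) = 0.931. These reproduce the stated values of about 80% and over 90%, but neither bears on QOL.

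**Assumptions, none from the documents.** Score 0–100, higher is better; SD 20; correlation r = 0.6 between Screening and follow-up scores; share p still on treatment at the later visit; correlation ρ between the follow-up score and staying on treatment. An EOS score is taken to stand in for the score the subject would have had at that visit.

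**Formulas.** With z = Φ⁻¹(1 − p) and true mean change 0:

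- Shift in the by-visit mean = ρ × SD × φ(z)/p.
- Bias in paired change among those still observed = that shift × (1 − r) = shift × 0.4.
- If half of those who left also supply an EOS score, the paired bias is multiplied by 0.5p / [p + 0.5(1 − p)], which is 0.41 at p = 0.7 and 0.33 at p = 0.5. If all supply one, the bias is 0.

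Example, p = 0.5 and ρ = 0.5: φ(0)/0.5 = 0.798; 0.5 × 20 × 0.798 = 8.0; paired 8.0 × 0.4 = 3.2; with half the EOS forms 3.2 × 0.33 = 1.1.

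**Results.** All columns were checked or obtained by simulation with 2,000,000 draws; the last two come from simulation and can differ from simple addition by 0.1.

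| p | ρ | By-visit shift, true change 0 | Paired, still observed | Paired, plus EOS for half of leavers | By-visit difference, true change −5 | By-visit difference, true change −10 |
|---|---|---|---|---|---|---|
| 0.7 | 0 | 0 | 0 | 0 | −5.0 | −10.0 |
| 0.7 | 0.3 | +3.0 | +1.2 | +0.5 | −2.0 | −7.0 |
| 0.7 | 0.5 | +5.0 | +2.0 | +0.8 | −0.1 | −5.0 |
| 0.5 | 0 | 0 | 0 | 0 | −5.0 | −10.0 |
| 0.5 | 0.3 | +4.8 | +1.9 | +0.6 | −0.2 | −5.2 |
| 0.5 | 0.5 | +8.0 | +3.2 | +1.1 | +3.0 | −2.0 |

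Of the 12 cells with a true decline, one shows an apparent improvement (+3.0). Where ρ is above 0, the others show a weakened or nearly vanished decline. A harsher setting (p = 0.3, ρ = 0.5, SD 25) gives a by-visit shift of 14.5.

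**Sampling error for comparison.** The 95% half-width for a mean is 1.96 × 20/√n: 8.8 at n = 20 and 12.4 at n = 10.

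**The case against.** The strongest reply has four parts.

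1. **Direction.** A reader might infer that dropout is bound to make QOL look better. The documents do not show that. They give no dropout rate, no QOL values and no link between the two. Progression is largely called on scheduled scans, and subjects with limited or borderline progression may stay on treatment and keep completing forms. With ρ = 0 there is no bias. An example in which ten subjects scoring 50 all leave and ten scoring 70 all stay moves the mean from 60 to 70 with nobody changing, but it assumes that dropout depends entirely on QOL. This part stands.

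2. **EOS.** A reader might infer that the SAP excludes the EOS form from analysis. It does not say so. The form is collected, EOS is a scheduled visit with QOL marked in Tables 4-1 and 4-2, and a by-visit table in all treated subjects could include it. The protocol is itself inconsistent, since its synopsis omits EOS too. This stands, but it leaves the programmer to choose between conflicting texts.

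3. **Change scores.** SAP Table 1 lists titles, not full table shells, and the SAP keeps change as the objective. That makes this under-specification, not a decision against change scores. It does not settle the matter, because four neighboring titles name change from baseline and this one does not.

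4. **Size.** Within the assumed range the shifts are smaller than the 95% half-width for 20 subjects, and QOL is descriptive. This limits the importance of the point. However, selection bias does not shrink as numbers grow, and the interval printed beside each mean does not account for it.

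**Conclusion.** The point holds as a gap in specification. The objective is change in QOL; no within-subject QOL change is defined in either document; and SAP 1.3.1.2, like the protocol synopsis, omits an assessment that the rest of the protocol requires. By-visit means from the on-treatment group can look like improvement or hide deterioration if subjects with worse QOL leave earlier. That condition is plausible, given why treatment ends, but the documents do not establish it. With SD 20, 50–70% retained and ρ from 0 to 0.5, the spurious upward shift is 0 to about 8 points; these inputs are assumptions. The claim that results will show improvement is not supported. This is a minor, easily corrected matter for a descriptive secondary endpoint.

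**What to change.** - Add the EOS questionnaire to SAP 1.3.1.2 and align the protocol synopsis with Sections 9.1.14 and 9.2.10 and Tables 4-1 and 4-2.
- In T 1.3.1, for each QLQ-C30 and QLQ-BN20 scale, report paired change from Screening (n, mean, 95% CI) at each visit and at EOS or last assessment. An EOS row of raw means would not be enough, because it describes only those who stopped.
- Show the number of forms expected and received at each visit.

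**Cost.** A few extra table columns from data already collected, with no effect on sample size or the primary analyses. Paired change among those still observed remains selected (up to +3.2 points in the table above), and EOS helps only as far as forms are returned, so the results still need cautious reading.

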### 1.3.1.3 Exploratory Endpoints

- For Cohort B, decreases in NSCLC cells in the CSF using rare cell capture techniques
- For Cohort B, decreases in CSF cell-free DNA
- For Cohort B, To utilize CSF cell-free DNA to detect activating EGFR mutations

#### 1.3.2 Safety Assessments

The NCI CTCAE; Version 5 will be used for grading toxicities. Safety assessments will include adverse events (AEs), serious adverse events (SAEs), physical examinations, vital sign measurements, clinical safety laboratory evaluations (hematology, serum chemistry, and urinalysis), Eastern Cooperative Oncology Group (ECOG) scores, and electrocardiograms (ECGs).

The AE reporting period for a subject enrolled in the study begins when the subject provides informed consent and is continued through 30 days after the last dose of

study drug or until start of new treatment. All AEs that occur in enrolled subjects during the AE reporting period specified in the protocol must be recorded, regardless of the relationship of the AE to study drug. Any known untoward event that occurs beyond the AE reporting period that the investigator assesses as possibly related to tesevatinib should be included.

Vital sign measurements, including sitting blood pressure, pulse rate, respiratory rate, and temperature will be monitored throughout the study.

# 1.3.3 Pharmacokinetic Endpoints

For subjects in Cohort B

- Plasma and CSF PK samples will be obtained on Cycle 1 Day 14 and on Cycle 3 Day 1, within approximately 4–8 hours after tesevatinib administration
- Plasma PK sample will be obtained at predose on Day 14 of Cycle 1 and at predose on Day 1 of Cycle 3

Tesevatinib concentrations in the plasma and CSF will be summarized at each scheduled collection time point using descriptive statistics, and displayed graphically

## 1.3.4 Pharmacodynamic Endpoints

Some pharmacodynamics endpoints have been included as exploratory endpoints.

## 2 Statistical Methods

No formal hypothesis testing will be conducted. Descriptive statistics including 95% confidence intervals for response rate, time-to-event and continuous measurements will be summarized by cohorts.

Tesevatinib concentrations in the plasma and CSF will be summarized at each scheduled collection time point using descriptive statistics, and displayed graphically.

AEs, SAEs, Grade 3&4 AEs, related AEs, related SAEs, related Grade 3&4 AEs, death, and AEs leading to withdrawal, dose modification, or treatment discontinuation will be summarized by cohort and overall according to high level terms (HLT) and preferred terms (PT). Adverse events will also be summarized in listings. Duration of AEs will be determined and included in listings, along with action taken and outcome.

Vital sign measurements will be summarized at each scheduled time point using descriptive statistics. The ECOG performance status results will be summarized by scheduled time point.

Laboratory results will be classified according to NCI-CTCAE Version 4.03 and summarized by cohort. The worst on-study grade after the first dose of study drug will be summarized. The incidence of ≥ Grade 3 laboratory abnormalities under treatment and shifts in toxicity grading from Cycle 1 Day 1 to highest grade post-Cycle 1 Day 1 will be displayed. Results for variables that are not coded will be presented in the listings as below, within, and above the normal limits of the local laboratory.

The table of list of tables, listings, and figures is displayed in Table 1.

 Table 1 Content of efficacy tables

| T/F/L | Number | Title   | Order                        | Population                    | Summary Statistics            |
|-------|--------|---|------------------------------|-------------------------------|-------------------------------|
| T     | 1.1.1  | Response rate by cohort   | Primary efficacy             | All treated subjects          | ORR, CR, PR, exact CI         |
| Т     | 1.1.2  | Response rate by visit and cohort                                   | Primary efficacy             | All treated subjects          | ORR, CR, PR, exact CI         |
| L     | 1.1.1  | Tumor size / symptoms and signs by visit and cohort                 | Primary efficacy             | All treated subjects          |                               |
| Т     | 1.2.1  | Progression-free survival (PFS) by cohort                           | Secondary efficacy           | All treated subjects          | descriptive statistics        |
| Т     | 1.2.2  | Overall survival (OS) by cohort                                     | Secondary efficacy           | All treated subjects          | descriptive statistics        |
| Т     | 1.2.3  | non-CNS time to progression by cohort                               | Secondary efficacy           | All treated subjects          | descriptive statistics        |
| Т     | 1.2.4  | CNS time to progression by cohort                                   | Secondary efficacy           | All treated subjects          | descriptive statistics        |
| F     | 1.2.1  | Progression-free survival (PFS) by cohort                           | Secondary efficacy           | All treated subjects          | KM curve                      |
| F     | 1.2.2  | Overall survival (OS) by cohort                                     | Secondary efficacy           | All treated subjects          | KM curve                      |
| F     | 1.2.3  | non-CNS time to progression by cohort                               | Secondary efficacy           | All treated subjects          | KM curve                      |
| F     | 1.2.4  | CNS time to progression by cohort                                   | Secondary efficacy           | All treated subjects          | KM curve                      |
| Т     | 1.3.1  | QOL by visit and cohort   | Secondary efficacy           | All treated subjects          | Descriptive Statistics |
| L     | 1.4.1  | NSCLC cells in the CSF using standard cytology by visits            | Secondary efficacy           | All treated cohort B subjects | Descriptive Statistics |
| Т     | 1.4.2  | CNS MRI findings by visits and change from baseline                 | Secondary efficacy           | All treated cohort B subjects | Descriptive Statistics |
| L     | 1.4.2  | CNS MRI findings by visits  | Secondary efficacy           | All treated cohort B subjects | source date                   |
| L     | 1.5.1  | NSCLC cells in the CSF using rare cell capture techniques by visits | Exploratory Endpoints | All treated cohort B subjects | source date                   |
| L     | 1.5.2  | CSF cell-free DNA by visits   | Exploratory Endpoints | All treated cohort B subjects | source date                   |
| L     | 1.5.3  | EGFR mutations by visits  | Exploratory Endpoints | All treated cohort B subjects | source date                   |
| Т     | 1.6.1  | Plasma concentration by visit                                       | PK                           | All treated cohort B subjects | Descriptive Statistics        |
| L     | 1.6.1  | Plasma concentration by subject and visit                           | PK                           | All treated cohort B subjects | source date                   |
| F     | 1.6.1  | Plasma concentration by subject and visit                           | PK                           | All treated cohort B subjects | source date                   |
| T     | 1.6.2  | CSF concentration by visit  | PK                           | All treated cohort B subjects | Descriptive Statistics |
| L     | 1.6.2  | CSF concentration by subject and visit                              | PK                           | All treated cohort B subjects | Descriptive Statistics        |

| F                                | 1.6.2 CSF cond | entration by su | bject and visit             | PK                             | All treated cohort B subjects source date |  |
|----------------------------------|----------------|-----------------|-----------------------------|--------------------------------|---|--|
| Table 2 Content of safety tables |                |                 |                             |                                |   |  |
| T/F/L                            | Part           | Number          | Title                       |                                | Population                                |  |
| Т                                | Disposition    | 1.1.1           | Patient disposition by coho | rt                             | All enrolled patients                     |  |
| L                                | Disposition    | 1.1.1           | Patient disposition         |                                | All enrolled patients                     |  |
| L                                | Disposition    | 1.2.1           | Protocol deviations         |                                | All enrolled patients                     |  |
| Т                                | Demo           | 2.1.1           | Demographics and baseline   | e characteristics by cohort    | All treated patients                      |  |
| L                                | Demo           | 2.1.1           | Demographics and baseline   | e characteristics              | All treated patients                      |  |
| L                                | Demo           | 2.2.1           | Medical history             |                                | All treated patients                      |  |
| L                                | Demo           | 2.3.1           | Disease history             |                                | All treated patients                      |  |
| L                                | CM             | 3.1.1           | Prior and concomitant med   | lications                      | All treated patients                      |  |
| Т                                | Exposure       | 4.1.1           | Treatment exposure and co   | ompliance by cohort            | All treated patients                      |  |
| L                                | Exposure       | 4.1.1           | Treatment exposure and co   | ompliance                      | All treated patients                      |  |
| L                                | Exposure       | 4.2.1           | Dose modifications          |                                | All treated patients                      |  |
| Т                                | AE             | 6.1.1           | Overall summary of TEAEs    | by cohort                      | All treated patients                      |  |
| Т                                | AE             | 6.1.2           | TEAEs by SOC/PT and coho    | rt                             | All treated patients                      |  |
| Т                                | AE             | 6.1.3           | Treatment related AEs by S  | OC/PT and cohort               | All treated patients                      |  |
| Т                                | AE             | 6.1.4           | Serious TEAEs by SOC/ PT a  | nd cohort                      | All treated patients                      |  |
| Т                                | AE             | 6.1.5           | Serious Treatment Related   | AEs by SOC/PT and cohort       | All treated patients                      |  |
| Т                                | AE             | 6.1.6           | Grade 3 and 4 TEAEs by SO   | C/PT and cohort                | All treated patients                      |  |
| Т                                | AE             | 6.1.7           | Treatment Related Grade 3   | and 4 AEs by SOC/PT and cohort | All treated patients                      |  |
| Т                                | AE             | 6.1.8           | TEAEs by HLT and cohort     |                                | All treated patients                      |  |
| Т                                | AE             | 6.1.9           | Treatment related AEs by F  | ILT and cohort                 | All treated patients                      |  |
| T                                | AE             | 6.1.10          | Grade 3 and 4 TEAEs by HL   | T and cohort                   | All treated patients                      |  |
| Т                                | AE             | 6.1.11          | Treatment Related Grade 3   | and 4 AEs by HLT and cohort    | All treated patients                      |  |
| L                                | AE             | 6.1.1           | AEs                         |                                | All treated patients                      |  |
|                                  |                |                 |                             |                                |   |  |

